The FERDINAND Study builds on the previous PANaMAH programme, and significantly extends into a longer-term 6 month intervention in a larger multi-ethnic cohort of 'at risk' adults; with the aim of evaluating a F&B product that may contribute to improved glycaemia during both weight/adipose mass loss and longer-term weight loss maintenance. Plant-derived polyphenols, commonly found in fruits such as feijoa, may provide a novel nutrition approach with evidence from prior pre-clinical, and a human clinical study, demonstrating improvement in glycaemic parameters following short-term consumption of 150 mg/d commercially available whole feijoa powder. Use of machine-learning algorithms will integrate clinical responses and 'omics outputs to predict individual response to the intervention, and will include quantitative measurements of personalised postprandial glucose response (PPGR) to determine between-individual variability, and identify baseline parameters that predict this variability. The outcomes of PPGR from the FERDINAND Cohort, following 6 months consumption of feijoa whole fruit powder, will provide predictive algorithms that can be validated in a future follow-up assessment.

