2. STUDY OBJECTIVE

The objective of this study is to investigate the long-term effects of whole fruit feijoa powder, both during and following LED-driven weight loss on established and novel biomarkers of T2D, using an integrated systems nutrition approach; in a parallel design, RCT of 6 months duration, in a high risk multi-ethnic population with pre-diabetes resident in New Zealand.

Also, to develop a machine-learning algorithm that predicts PPGR in a sub-cohort of participants undergoing the longitudinal 6-month intervention; so that the predictive PPGR algorithm can be tested in a future study.

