	CID1 M0	CID 2 M2	CID 3 M4	CID 4 M6
Demographics	X			
Height	X			
Body weight	X	X	X	X
Waist circumference	X	X	X	X
Blood pressure	X	X	X	X
Fasting blood sample	X	X	X	X
Concomitant medications	X	X	X	X
Adverse events	X	X	X	X
Questionnaires (e.g. QoL and *Bristol stool chart)	X *	X *	X	X *
DXA, body composition	X	X	X	X
MRI/MRS, pancreas & liver fat (subgroup, n = 30)	X (n=15 placebo + n=15 whole fruit powder arm)	X (n=15 placebo + n=15 whole fruit powder arm)		X (n=15 placebo + n=15 whole fruit powder arm)
Mixed meal tests (MMT) over 3 consecutive days, CGM; at home	X			X (subgroup; n=40 placebo + n=40 whole fruit powder intervention arm)
2-hr OGTT, CGM; in clinic	X	X (subgroup; n=40 placebo + n=40 whole fruit powder intervention arm)		X (subgroup; n=40 placebo + n=40 whole fruit powder intervention arm)
Physical activity/steps	X	X	X	X
Indirect calorimetry, IC (subgroup, n = 30)	X (subgroup; n=15 placebo + n=15 whole fruit powder intervention arm)	X (subgroup; n=15 placebo + n=15 whole fruit powder intervention arm)		X (subgroup; n=15 placebo + n=15 whole fruit powder intervention arm)
Diet diary, self-reported	X	X	X	X
24-h urine sample [N], diet compliance	X	X	X	X
Faecal sample collection	X	X		X

GROUP VISITS – a total of 9 group visits (Phase 1, LED: Week 0, 2, 4, 6, and 8; Phase 2, Maintenance: Month 3, 4, 5, and 6), combination of in person or via virtual mHealth platform will be conducted by dietitians throughout the intervention to provide dietary advice and support to maximise compliance and treatment success.

PARTICIPANTS

N = 80 per intervention group

Total sample size of 160 participants

INCLUSION

- Male and female
- Aged between 18 - 70 years
- BMI \geq 26 kg/m² and body weight \leq 150kg
- FPG in prediabetic range, 5.6 – 6.9 mmol/L
- Otherwise healthy, as per self-report
- Agreement to participate in a weight loss study

EXCLUSION

- Type 1 or type 2 diabetes mellitus
- Medications controlling glycaemia
- Current or history of significant disease including cardiovascular disease; pancreatic disease, or other digestive diseases including inflammatory bowel syndrome/disease, ulcerative colitis, Crohn's disease; cancer; plus associated medications including steroids (except topical steroids) and atypical antipsychotics in previous 3 months
- Recent body weight loss/gain > 10 % within previous 3 months or taking part in an active diet program; or current medications for weight loss; or intending to alter physical activity during following 12 months

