All participants will be fasted overnight prior to attending the screening visit at the HNU clinic, Mount Eden, Auckland. During the screening visit, a participant information sheet (PIS) will be provided to individuals and the study will be explained by the research staff. Written informed consent will be obtained from each of the participants. They will then be screened for eligibility. Demographics (age, gender, and ethnicity), medical history, current medication and supplement intake will be recorded. Anthropometry (height, body weight, waist and hip circumference, BMI and blood pressure) will be recorded. A fasting blood sample will be conducted to assess FPG.

If participants are eligible they will be enrolled into the study and randomised, using the online Research Electronic Data Capture (REDCap) secure web-based system, to one of the two intervention arms. Following this, they will then be scheduled to attend a pre-intervention assessment visit.

VISIT 2- PRE-INTERVENTION ASSESSMENTS ['HOMEWORK' PRIOR TO START OF CID1]

Prior to CID 1/baseline participants will complete a series of pre-intervention assessments, during a 2 week window. Written and verbal instruction, including video call, will be provided to participants for each assessment. These will include

- DXA, body composition scan
 - MRI/MRS scan for pancreas and liver fat assessment
 - collection of faecal sample for microbiome analysis
 - 4 day weighed food record/24-h diet recall
 - 3 day MMT assessment (CGM inserted 3 days prior to CID 1)
 - 3 day PA assessment
- **(i) Body composition**
Total and compartmental body fat, pancreas fat and liver fat content will be characterised using:

Dual energy x-ray absorptiometry [DXA]

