(iv) Postprandial glucose response using CGM

Three 2-hr mixed meal tests (MMTs) will be conducted as described in Figure 2, to assess PPGR, using a CGM (the New Zealand Freestyle Libre System (Abbot, NZ) or similar). These are a lancet-free, single use units which typically comprise a Reader and Sensor, with ability to store data over 14 day intervals. The LibreView

software, or similar, will be used to analyse the data, and comprises a secure cloud-based system.

The CGM will be inserted prior to the start of the MMT and remain in situ throughout the assessment period (Figure 2). Three breakfast meals, one for each of the days, of fixed composition and each containing 50g available CHO will be used:

- Breakfast meal Day 1 (1MJ) – white bread, 50g available CHO
- Breakfast meal Day 2 (1MJ) – white rice, 50g available CHO
- Breakfast meal Day 3 (1MJ) – high fibre/ β -glucan, e.g. oats, 50g CHO

The meal will be consumed at home at 0800h, over a 15 minute interval. All breakfast foods must be consumed in full, no other foods consumed, and participant to remain sedentary over the 2-hr test. Postprandial glucose from the interstitial fluid (ISF-G) will be recorded throughout the 2-hour test. The CGM will remain in situ and measurements recorded continually throughout the day.

(v) Physical activity (PA)

PA will be assessed through record of daily step count, using the built-in accelerometer, gyroscope and GPS functions on the participant's personal smartphone device. The accuracy of tracking step counts using smartphone devices has been validated against routine wearable devices (Case, Burwick, Volpp, & Patel, 2015). The Apple iPhone 'Health' (<https://www.apple.com/nz/ios/health/>), Android 'Google Fit' app (<https://www.google.com/fit/>) or similar will be downloaded as free-ware. Participants will be requested to carry their smartphone throughout the 3-day MMT. Daily step count will be recorded, and data transferred to the HNU data hub when participants attend the HNU for their CID 1 visit. Alternatively, pedometers will be provided, by the researchers, to those participants without smartphone access.

VISIT 3 - CID 1/ WEEK 0/ BASELINE, START OF LED WEIGHT-LOSS (PHASE 1)

All participants will be fasted overnight prior to attending the study visit at the HNU. During the visit, the following will be conducted:

- Baseline assessments as outlined in Table 1. Including:
- 2-hr OGTT in all
- IC in subgroup; n=15 placebo arm & n=15 whole fruit powder arm

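### The three home test breakfasts are given in one fixed order, so meal type cannot be separated from test day in the data that feed the PPGR algorithm

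*Protocol*

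**What the plan says.** Protocol section 3, Visit 2, item (iv) sets out the meals: "Three breakfast meals, one for each of the days, of fixed composition and each containing 50g available CHO will be used". Each is tied to a numbered day: "Breakfast meal Day 1 (1MJ) – white bread, 50g available CHO", "Breakfast meal Day 2 (1MJ) – white rice, 50g available CHO" and "Breakfast meal Day 3 (1MJ) – high fibre" (oats are the example given). Table 1 describes the tests as "Mixed meal tests (MMT) over 3 consecutive days, CGM; at home". No random, rotated or counterbalanced order appears anywhere in the protocol.

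On sensor timing, the Visit 2 list has "3 day MMT assessment (CGM inserted 3 days prior to CID 1". The account of the 4-day procedure in section 3.1 puts Days 1 to 3 at home and Day 4 in clinic for the OGTT, which is the CID 1 visit.

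On use of the data, the opening summary says PPGR is measured "to determine between-individual variability, and identify baseline parameters that predict this variability". Section 2 makes a machine-learning PPGR algorithm the second objective, "so that the predictive PPGR algorithm can be tested in a future study". Section 3.1 lists the meal-test responses among the inputs to that model, and Outcome Variables lists the 2-h CGM glucose from the meal tests as a secondary outcome.

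On month 6, Table 1 and the text just before Phase 1 give the meal tests to 40 participants per arm. Visit 6 gives them only to the whole fruit powder group.

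**The concern.** Each person eats each meal once, and everyone eats them in the same sequence. Whatever differs between Days 1, 2 and 3 (age of the sensor, practice with the home procedure, carry-over from the previous day's test meal) is attached to one meal for the whole cohort. The refined-versus-high-fibre comparison is also a first-days-versus-third-day comparison.

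At stake are any statement that one breakfast raises glucose more than another, and any person-by-meal pattern that the algorithm picks up. A baseline characteristic that predicts how someone performs on the first test day cannot be told apart from one that predicts the response to bread. Because the order is fixed when the data are collected, this is not something that a later analysis plan can repair.

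**Working it through.** **1. The protocol's own figure.** It gives no number for the meal tests. The only sample size is for FPG: difference 0.3 mmol/L, SD 0.6 mmol/L, alpha 0.05 (taken as two-sided), power 80%. The normal approximation is n = 2 × (1.960 + 0.842)² × 0.6² / 0.3² = 62.8, so 63 per group. The t-test version gives 63.77, so 64, and 64 / 0.80 = 80. The stated 64 and 80 per group reproduce, and the meal order does not touch them.

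**2. The aliasing.** Write the response of person i to meal m on day d as person(i) + meal(m) + day(d) + error. With one order, d is determined by m, so

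bread − rice (observed) = [meal(bread) − meal(rice)] + [day(1) − day(2)].

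The two brackets never occur apart. Rank of the fixed-effects design (participant + 2 meal columns + 2 day columns):

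| Order | N | Columns | Rank | SE of a meal contrast (σ = within-person SD) |
|---|---|---|---|---|
| Fixed, as planned | 160 | 164 | 162 | not estimable with day in the model; √(2/160) = 0.112σ if day is ignored |
| Fixed, as planned | 80 | 84 | 82 | not estimable with day in the model; √(2/80) = 0.158σ if day is ignored |
| 3-sequence Latin square | 160 / 80 | 164 / 84 | full | 0.112σ / 0.158σ |
| All six orders | 160 / 80 | 164 / 84 | full | 0.112σ / 0.158σ |

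The deficiency of 2 is exactly the two meal contrasts, and it does not shrink with N. Balancing the order restores them at essentially no loss of precision.

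**3. Size under assumed values.** The protocol gives no size for a day or sensor-age effect, so these are assumptions. A Day 1 offset of d shifts bread minus rice by d: for d of 0.2 to 0.5 mmol/L, by 0.2 to 0.5. In a simulation with 40 per arm, no true bread-rice difference and day effects of +0.4, +0.1 and 0 mmol/L, rice minus bread should come out at 0.1 − 0.4 = −0.30; it came out at −0.299. An incremental area under the curve would remove a constant offset, but not a proportional error or carry-over.

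**4. What is not affected.** In the same simulation, with a true arm difference of −0.30, the estimate was −0.294 with the day effects and −0.305 without, both within simulation error. A day effect common to all cancels between arms that take the same tests, and between people compared on the same meal.

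**5. Sensor insertion.** If CID 1 is Day 4, three days earlier is Day 1, the bread day. This is an inference: item (iv) says only that insertion precedes the meal tests, no clock time is given, and Figure 2 is not available. If insertion were earlier, step 2 would stand unchanged.

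**The case against.** The strongest reply is that no bread-rice-oats contrast is an objective or a listed outcome. The stated purpose of PPGR is variation between individuals, and for that a fixed order has merit: everyone meets each meal at the same sensor age and after the same preceding meal. Randomising makes these differ between people within a meal, and a test-day term removes only the additive part. This stands as a real trade-off, and it is why the point is an improvement and not a fatal flaw. It does not remove the point. Person-specific day variation is present under either design; under the fixed order it is tied to one meal throughout, whereas a balanced order separates meal from day both on average and in their relation to baseline predictors.

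It can also be said that CGM runs continually and inter-day variability measures are planned, so overnight and non-test readings could partly reveal sensor drift. That is fair for the sensor component, but not for learning or carry-over. The protocol gives a venous reference only alongside the Day 4 OGTT, not on Days 1 to 3.

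A reader might infer more than the protocol supports:

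- That the algorithm will carry a day artefact into the future study. The meal schedule of that study is not given, and it could repeat this one.
- That bread is certainly read on a newly inserted sensor and that such a sensor reads differently. The first is inferred, and nothing in the protocol states the second.
- That the meal tests are a formal crossover with a planned between-meal test. The protocol does not say so.

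**Conclusion.** The point holds in limited form. Meal type and test day are completely aliased, and no later analysis can fully separate them. This affects differences between meals and person-by-meal responses in the PPGR algorithm, the second objective. The size of any resulting error is unknown; 0.2 to 0.5 mmol/L is an illustration under assumed offsets.

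It should not be read as a threat to the main trial result. FPG and body weight at 6 months, the sample size, and comparisons of people on the same meal are not biased by a day effect common to all. Nor should the month-6 arm comparison of meal tests be declared safe on the present text: that reassurance requires both arms to take the tests, and Visit 6 contradicts Table 1 on exactly this. Randomising the breakfast order is a cheap improvement that should be made.

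**What to change.** Randomise the breakfast order over the six possible sequences within each arm, using REDCap, which already allocates the arms before the Visit 2 assessments. That gives 80 / 6 ≈ 13 participants per sequence per arm. All six orders are preferable to a 3-sequence Latin square, which balances day but not the preceding meal. Keep each participant's own order at month 6, and include test day as a term in the PPGR model.

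The cost is one REDCap field, personally labelled meal packs, slightly more complex home instructions and a few order errors. Day and preceding meal will vary between people within a meal; the model term handles the additive part. No extra meals, sensors or visits are needed.

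Separately, reconcile Visit 6 (month-6 meal tests in the powder group only) with Table 1 and the text before Phase 1 (40 per arm). The sensor insertion time relative to the first breakfast should also be stated, and the section 3.1 description of a single standardised breakfast aligned with the three different meals in item (iv).

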The postprandial CGM assessments will be conducted prior to the start of the LED, i.e. 3 days prior to CID1/baseline visit in all participants; and similarly 3 days prior to CID4/8 months but only in the sub-group of participants randomised to the placebo and the feijoa whole fruit powder intervention arms (40 participants each arm; Table 1).

WEIGHT LOSS_LOW ENERGY DIET [LED]: PHASE 1

Commercial LED meal replacements (Cambridge Weight Plan™ Ltd) will be consumed for 8 weeks throughout Phase 1. LED is energy restricted with a target intake of ~4MJ/day. The target macronutrient composition of the diet will be 15-20% of total energy from fat, 35-40% from protein and 45-50% from carbohydrate. LED products include shakes, soups, bars, porridge, pasta and savoury meals.

- Participants randomised to the Healthy diet/weight loss advice + feijoa whole fruit powder arm will receive the LED products to be consumed as a total meal replacement with the whole fruit powder to be supplemented into the diet and consumed alongside the LED, with target EI of 4MJ/day.
- Participants randomised to Healthy diet/weight loss advice + matched Placebo arm will receive the LED products to be consumed as a total meal replacement with the matched placebo to be supplemented into the diet and consumed alongside the LED, with target EI of 4MJ/day.

During Phase 1 participants will attend, either in person or via virtual online mHealth platform, 5 group meetings delivered from the HNU clinic site. At each group meeting, adverse events (AE) and concomitant medications will be recorded; and dietary advice and behavioural instructions provided by dietitians. Participants will be recommended to maintain PA as per baseline (no increase) during the LED weight-loss phase. All participants will remain on the LED until their CID2 visit at week 8. It is expected that weight loss over 8 weeks will be between 5-10% of baseline body weight.

WEIGHT MAINTENANCE_DIETARY INTERVENTION: PHASE 2

During Phase 2 (4 months) participants will attend, either in person or via virtual mHealth platform, 4 group meetings delivered from the research site. The dietary advice will adhere to the New Zealand Ministry of Health healthy eating guidelines (McIntyre & Dutton, 2015) for improving metabolic health, with diet advice provided by dietitians.

CLINIC ASSESSMENTS

TABLE 1. SUMMARY OF CID ASSESSMENTS OVER THE 6 MONTH STUDY PERIOD

Assessments	Phase 1 - LED		Phase 2- Maintenance	

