Metabolomics analyses will be conducted at the Mass Spectrometry facility of AgResearch Ltd, Palmerston North (<https://www.agresearch.co.nz/metabolomics>).

A combination of multiple extraction solvents and analyses optimised for different metabolite polarity classes i.e. lipids, polar compounds such as amino acids, nucleotides etc., will be used. High resolution LCMS streams will be used for polar, semi-polar and non-polar metabolites, and GCMS for other polar metabolites not measurable by LCMS. Identifications performed using in-house and external libraries, plus high resolution MS/MS to determine metabolite class, molecular formula for identification where required. Polar/semi-polar metabolites will be extracted from plasma and measured by LCMS using HILIC (hydrophilic interaction liquid chromatography) system coupled to high resolution Orbitrap MS detector; also TMS derivatisation and metabolites measured by GCMS; also LCMS using C18 (reverse phase) chromatography system coupled to a high resolution Orbitrap MS detector. Non-polar metabolites will be extracted from plasma and measured by LCMS using a CSH (modified reverse phase) chromatography system coupled to high resolution Orbitrap MS detector. In addition to high resolution detection of the molecular ion, this analytical system will collect fragmentation spectra of the major non-polar components to enable *in-silico* identification using the Thermo Lipid Search software package.

OUTCOME VARIABLES

Co-Primary outcomes

- fasting plasma glucose (FPG) at 6 months
- body weight at 6 months

Secondary outcomes

- HbA_{1c},
- postprandial 2-h CGM-assessed ISF-G
 - a. MMT
 - b. OGTT
- body composition including:
 - a. total body fat (DXA),
 - b. abdominal body fat (MRI, sub-group)
 - c. pancreas fat (MRI, sub-group)
 - d. liver fat (MRS, sub-group)
- plasma metabolome profile
- indirect calorimetry (IC, sub-group) including:
 - a. resting metabolic rate
 - b. glucose-induced thermogenesis

Other outcomes

- clinical biomarkers including:
 - OGTT venous glucose, fasting and OGTT insulin, C-peptide, lipid profile (total cholesterol, LDL-C, HDL-C, triglyceride), liver function tests, inflammatory & immune markers
- faecal microbiome
- urine Nitrogen (dietary compliance)
- epigenetic, SNP, miRNA markers of T2D
- PA assessment (step count)

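### Baseline steps are counted on the three mixed-meal-test days, under a 2-hour sedentary rule that later visits do not share, so within-person change in activity may be biased upward

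*Protocol*

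**What the plan says.** All references are to Protocol section 3.1.

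- **Measure.** Visit 2, item (v): "PA will be assessed through record of daily step count". The measure is whole-day steps.
- **Baseline days.** The same item fixes when: "Participants will be requested to carry their smartphone throughout the 3-day MMT".
- **Restriction on those days.** Visit 2, item (iv) sets a breakfast at 0800h on each of three days, with "no other foods consumed, and participant to remain sedentary over the 2-hr test".
- **Who is restricted at baseline.** The section on baseline phenotype places the CGM and meal assessments "3 days prior to CID1/baseline visit in all participants", so both arms are covered in full.
- **Later visits.** Table 1 marks steps at CID 1, 2, 3 and 4. Its row "Mixed meal tests (MMT) over 3 consecutive days, CGM; at home" is marked at CID 1 for everyone and at CID 4 for 40 placebo and 40 powder participants; it is blank at CID 2 and CID 3. The Visit 4 and Visit 5 lists include a three-day activity assessment and no meal test. Neither says which days are meant, and Visit 4 refers back to methods already described.
- **Conflicting statements on the meal tests.** The notes to Figure 1 name meal tests among the CGM assessments and give a CID 2 sub-group of 40 + 40. The Visit 6 list confines the CID 4 meal tests to the powder group.
- **Use of the data.** Step count is listed under Other outcomes. Under Phase 1: "Participants will be recommended to maintain PA as per baseline (no increase) during the LED weight-loss phase".

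**The concern.** A repeated measure of habitual activity should be taken under the same conditions each time. Here the reference value is taken on days when the study itself removes 2 hours of movement, while at CID 2 and CID 3, on the Table 1 schedule, nothing is removed. A participant whose habits have not changed may then seem to have become more active during the low energy diet, the phase in which activity is meant to stay level.

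The only activity method the Protocol describes is tied to the meal-test days, so it cannot be applied as written at visits without a meal test. This is a rule for collecting data. If unrestricted baseline days are not recorded, no later analysis can recover them.

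At stake are the step-count outcome as a within-person change, and any reading of it as evidence that activity stayed at its baseline level.

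**Working it through.** **Stated figure.** The Protocol gives no figure for step count: no mean, no SD, no time-of-day profile. Its sample-size calculation concerns FPG and does not enter here.

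**Step 1: conditions at each visit**

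| Visit | Steps recorded | Participants under the 2-h rule on the step days |
|---|---|---|
| CID 1 | yes | all 160 |
| CID 2 | yes | none (Table 1, baseline-phenotype section, Visit 4); 80 of 160 if the Figure 1 notes are read as placing meal tests there |
| CID 3 | yes | none |
| CID 4 | yes | 40 + 40 (Table 1, baseline-phenotype section) or powder group only (Visit 6) |

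For CID 4 this supposes that the step days are the meal-test days, as at baseline.

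**Step 2: apparent change when true activity is constant**

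Let *s* be the share of usual daily steps that falls in the 2-hour window, and *c* the share of those made up later the same day. Both are assumptions.

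- Baseline steps / usual steps = 1 − *s*(1 − *c*)
- Apparent change at a visit without meal tests = 1 / [1 − *s*(1 − *c*)] − 1

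With 16 waking hours and evenly spread steps, *s* = 2/16 = 12.5%. Values of 5% and 20% bracket it.

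| *s* | *c* = 0 | *c* = 0.5 | *c* = 1 |
|---|---|---|---|
| 5% | 1/0.95 − 1 = +5.3% | 1/0.975 − 1 = +2.6% | 0% |
| 12.5% | 1/0.875 − 1 = +14.3% | 1/0.9375 − 1 = +6.7% | 0% |
| 20% | 1/0.80 − 1 = +25.0% | 1/0.90 − 1 = +11.1% | 0% |

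**Step 3: if half the cohort had meal tests at CID 2**

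At *s* = 12.5% and *c* = 0, tested participants show no artefact and the rest show +14.3%. The average is 0.5 × 0 + 0.5 × 14.3 = about +7.1%. The mismatch shrinks but remains, and CID 3 is unaffected by this reading.

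**Step 4: between-arm difference in steps**

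With no make-up, the expected powder-minus-placebo difference, as a percentage of usual steps, is −*s* × (*f*₁ − *f*₀), where *f*₁ and *f*₀ are the shares of the powder and placebo arms under the 2-h rule.

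- CID 2 and CID 3: both arms share the same baseline procedure and *f*₁ = *f*₀, so the difference is 0.
- CID 4, 40 + 40: *f*₁ = *f*₀ = 40/80 = 0.5, so the difference is 0.
- CID 4, powder group only:

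| *s* | 40 of 80 tested (*f*₁ = 0.5, *f*₀ = 0) | all 80 tested (*f*₁ = 1, *f*₀ = 0) |
|---|---|---|
| 5% | −2.5% | −5% |
| 12.5% | −6.25% | −12.5% |
| 20% | −10% | −20% |

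**The case against.** **The timing has a purpose.** The Background names physical activity as a predictor of the postprandial glucose response, and Figure 2 places step counting inside the four-day glucose protocol. For that use, steps on the meal-test days are the right input. This stands, and is a reason to keep those steps. It does not make them a suitable baseline for a repeated outcome whose later values come from other days.

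**The bias is not shown.** The measure is whole-day steps, and nothing in the Protocol says how many usually fall between 0800h and 1000h or whether they are made up afterwards. This also stands. A reader might infer that baseline activity is certainly understated, or understated by a known percentage; the Protocol supports only a likely direction.

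**The consequences can be overdrawn.** A reader might infer that a planned check on constant activity fails, or that changes in weight or FPG would be wrongly credited to activity. The Protocol defines no such check and no analysis that attributes outcome change to steps. The Phase 1 sentence is advice to participants, and it does not say that the three-day count is the level they are held to.

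**The schedule is itself contested.** One cannot say flatly that CID 2 has no meal tests, that 80 participants have them at CID 4, or that the artefact is common to both arms at every visit. The Figure 1 notes and the Visit 6 list stand against these statements.

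**Conclusion.** The point holds as a minor one. Baseline steps are recorded under a restriction that covers all participants, while follow-up steps are recorded under no restriction or a partial one. Baseline activity is likely understated, because the restriction takes steps out of the window and only full make-up later in the day cancels the loss. Within-person change may therefore be biased upward. The amount depends on two quantities the Protocol does not give: 0% with full make-up, about 14% at 2 of 16 waking hours with even spread and no make-up, and up to 25% in the range tried.

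The co-primary outcomes are not touched, and the randomised comparison of steps at CID 2 and CID 3 is not biased in expectation. The exception is CID 4: if the meal tests are done only in the powder group, the step comparison could differ by arm, by 2.5% to 20% of usual steps under the assumed inputs with no make-up. Under the 40 + 40 schedule it would not.

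**What to change.** 1. Define the step-count outcome at every CID as the mean of three days without a test meal. At CID 1 and CID 4, take them in the existing two-week homework window before meal-test Day 1; three test days leave up to 14 − 3 = 11 days to choose from. At CID 2 and CID 3, take three days before the visit that carry no test meal.
2. Keep the meal-test-day steps as a separate variable, used as the activity input to the PPGR model.
3. Reconcile the meal-test schedule: for CID 2, the Figure 1 notes against Table 1, the baseline-phenotype section and the Visit 4 list; for CID 4, the Visit 6 list against Table 1 and the baseline-phenotype section.

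Phones log steps passively and the windows already exist, so for most participants the change is one of wording. The cost falls on those without a smartphone: about three more pedometer days at CID 1 and at CID 4, with the pedometer handed out earlier.
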